5.6 Discussion and Justification of Study Design

5.6.1 Discussion of Study Design and Choice of Control Arms

This study is an open-label pilot study designed to evaluate the safety, tolerability, pharmacokinetics, and antiviral activity of ombitasvir/ABT-450/r dosed in combination with SOF with or without RBV. The study will also provide information on the role of RBV with this regimen, the pharmacokinetics of ombitasvir/ABT-450/r and SOF with or without RBV in HCV-infected subject, the proportion of subjects achieving SVR₁₂, and the development and persistence of viral resistance with this treatment regimen.

High SVR rates have been reported in subjects with HCV genotype 3 infection treated with the combination of SOF and daclatasvir, another NS5A inhibitor, for 24 weeks.²³ Due to the presence of a third active agent, ABT-450, the treatment regimen in the current study is expected to have greater activity than that seen with SOF and daclatasvir; thus a greater treatment response is anticipated. The treatment duration for this study was selected based upon viral load modeling and simulations. Data for ABT-450/r + ombitasvir ± RBV in HCV genotype 3-infected subjects enrolled into Study [REDACTED] were modeled, as well as data for [REDACTED].

Since [REDACTED] in vitro potency is similar between genotypes 1 and 3, genotype 1 parameters were used to simulate the response in subjects infected with HCV genotype 3 infection. SVR for the combination of ABT-450/r + ombitasvir + SOF ± RBV was simulated using model parameters from the [REDACTED] analyses. Based upon these simulations, >[REDACTED] % of subjects receiving 2DAA + SOF ± RBV for 12 weeks are predicted to achieve SVR₁₂ while treatment durations less than 12 weeks are predicted to result in a greater number of relapses. Hence, 12 weeks of dosing is planned.

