4.2 Design Diagram

This is a Phase 2, randomized, open-label, multicenter study evaluating the efficacy and safety of co-administration of ombitasvir/ABT-450/r with SOF with or without RBV administered for 12 weeks in HCV GT3 (with and without cirrhosis) and 8 and 6 weeks for GT2 (without cirrhosis) infected, treatment-naïve and treatment-experienced (previous pegIFN/RBV and/or SOF) adults. Approximately 70 subjects will be enrolled at approximately 8 sites globally.

[figure not shown]
Treatment Period and Post-Treatment Period

Approximately 20 GT3 subjects without cirrhosis meeting the eligibility criteria will be randomized 1:1 into Arm A and Arm B and treated as below:

- Arm A: ombitasvir/ABT-450/ritonavir 25/150/100 mg once daily (QD) and SOF 400 mg (QD) for 12 weeks;
- Arm B: ombitasvir/ABT-450/ritonavir 25/150/100 mg once daily (QD) and SOF 400 mg (QD) with RBV 1000 – 1200 mg divided twice daily (BID) per local label for 12 weeks.

Randomization to Arms A and B will be stratified by IL28B genotype (CC versus non-CC) and prior treatment status (treatment-naïve versus treatment-experienced).

Approximately 10 GT2 subjects meeting the eligibility criteria will be enrolled in to each of Arm C and Arm D and treated as described below. Arm D would be launched if no more than one subject who completes treatment in Arm C experiences relapse through PT Week 4.

Figure 1. Study Schematic

- Arm C: ombitasvir/ABT-450/ritonavir 25/150/100 mg once daily (QD) and SOF 400 mg (QD) with weight based RBV 1000 – 1200 mg BID per local label for 8 weeks;

- Arm D: ombitasvir/ABT-450/ritonavir 25/150/100 mg once daily (QD) and SOF 400 mg (QD) with weight based RBV 1000 – 1200 mg BID per local label for 6 weeks;

Approximately 20 subjects with genotype 3 HCV infection with compensated cirrhosis (a minimum of approximately 20% will be treatment-experienced) will be enrolled into Arm E:

- Arm E: ombitasvir/ABT-450/r 25 mg/150 mg/100 mg and SOF 400 mg QD with RBV 1000 – 1200 mg BID for 12 weeks

An additional 10 subjects with genotype 3 HCV infection without cirrhosis will be enrolled in open-label fashion into Arm F:

- Arm F: ombitasvir/ABT-450/r 25 mg/150 mg/100 mg and SOF 400 mg QD for 12 weeks

RBV dosing will be weight-based, either 1000 mg or 1200 mg daily divided BID per local label (e.g., < 75 kg = 1000 mg daily divided BID or ≥ 75 kg = 1200 mg daily divided BID).

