Note: Data must also have Study Drug End Day ≤ 2 for all windows. The result closest to the scheduled time point will be used. Child-Pugh classification (for cirrhotic subjects only), FibroTest are collected at Screening and Week 12 (or upon study discontinuation) and will use those visit windows as defined above. FibroTest is also collected at baseline, only if not performed at the time of screening.

Table 3. Analysis Time Windows for HCV RNA, Resistance Endpoints, Laboratory Data, and Vital Sign (Treatment Period) for 8-Week of Treatment

Scheduled Visit	Nominal Day (Study Day)	Time Window (Study Day Range)
Day 1/Baseline ^a	1 ^a	≤ 1 ^a
Week 1	7	2 to 10
Week 2	14	11 to 21
Week 4	28	22 to 42
Week 8	56	43 to 70
Final Treatment Visit ^b		2 to ≤ 2 days after last dose of study drug

a. Day of first dose of study drug.

b. The last value within the window will be used to define the Final Treatment visit value. The upper bound of this Final window is Study Drug End Day ≤ 2.

Note: Data must also have Study Drug End Day ≤ 2 for all windows. The result closest to the scheduled time point will be used.

Table 4. Analysis Time Windows for HCV RNA, Resistance Endpoints, Laboratory Data, and Vital Sign (Treatment Period) for 6-Week of Treatment

Scheduled Visit	Nominal Day (Study Day)	Time Window (Study Day Range)
Day 1/Baseline ^a	1 ^a	≤ 1 ^a
Week 1	7	2 to 10
Week 2	14	11 to 21
Week 4	28	22 to 35
Week 6	42	36 to 49
Final Treatment Visit ^b		2 to ≤ 2 days after last dose of study drug

a. Day of first dose of study drug.

b. The last value within the window will be used to define the Final Treatment visit value. The upper bound of this Final window is Study Drug End Day ≤ 2.

Note: Data must also have Study Drug End Day ≤ 2 for all windows. The result closest to the scheduled time point will be used.

Table 5. Analysis Time Windows for HCV RNA, Resistance Endpoints, (Post-Treatment Period)

Scheduled Visit ^a	Nominal Day (Study Drug End Day)	Time Window (Study Drug End Day Range)
Post-Treatment Week 2	14	3 to 21
Post-Treatment Week 4	28	22 to 42
Post-Treatment Week 8	56	43 to 77
Post-Treatment Week 12	84	78 to 126
Post-Treatment Week 24	168	127 to 210
Post-Treatment Week 36	252	211 to 294
Post-Treatment Week 48	336	295 to 378
SVR ₄ ^b	28	3 to 56
SVR ₁₂ ^b	84	57 to 126
SVR ₂₄ ^b	168	127 to 210

a. Post-Treatment Visits are applicable for subjects who received at least one dose of study drug.

b. For SVR windows, the last value in the window will be used.

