10.0 Efficacy Analysis

10.1 General Considerations

Analyses will be performed on the intent-to-treat (ITT) population. Sensitivity analyses of the primary endpoint, when applicable, will be performed on the mITT-GT-VF population specified in Section 5.1.1.

Missing data will be imputed as described in Section 6.3 for analyses of the HCV RNA endpoints of SVR.

Plasma HCV RNA levels will be determined for each sample collected by the central laboratory using the Roche COBAS TaqMan® real-time reverse transcriptase-PCR (RT-

PCR) assay v.2.0. For this assay, the lower limit of quantitation (LLOQ) is 25 IU/mL regardless of genotype, and the lower limit of detection (LLOD) varies by genotype. For GT3, the lower limit of detection (LLOD) is 20 IU/mL; for GT2, LLOD is 20 IU/mL. HCV RNA results that are detectable but not quantifiable are reported as "< 25 IU/mL HCV RNA detected" and those that are undetectable are reported as "HCV RNA not detected" in the database.

The notation "HCV RNA < LLOQ" is used to represent all HCV RNA values < 25 IU/mL, including values reported as "HCV RNA not detected" or "< 25 IU/mL HCV RNA detected." HCV RNA \geq LLOQ are all quantifiable values of 25 IU/mL or greater.

IL28B rs12979860 will be resulted as C/C, C/T, or T/T by the central laboratory.

Definitions for Efficacy Endpoints

Note that a confirmed quantifiable post-treatment value is defined as two consecutive post-treatment HCV RNA measurements \geq LLOQ. During treatment, a confirmed quantifiable value is defined as any two consecutive HCV RNA values \geq LLOQ, either both during treatment or at the final treatment measurement and the next consecutive post-treatment measurement.

Breakthrough = confirmed HCV RNA \geq LLOQ after HCV RNA < LLOQ during treatment, or confirmed increase from nadir in HCV RNA (two consecutive HCV RNA measurements $> 1 \log_{10}$ IU/mL above nadir) at any time point during treatment. A single breakthrough value (\geq LLOQ or $> 1 \log_{10}$ IU/mL above nadir) followed by lost to follow-up will be considered a breakthrough (i.e., will not require confirmation).

On-treatment virologic failure = breakthrough or failure to suppress during treatment (all on-treatment values of HCV RNA \geq LLOQ) with at least 6 weeks (defined as study drug duration \geq 36 days) of treatment for 12-week and 8-week treatment or at least 26 days of treatment for 6-week treatment.

RVR (rapid virologic response) = HCV RNA < LLOQ in the Week 4 window.

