EOTR (end of treatment response) = HCV RNA < LLOQ in the Week 12 window for 12-week regimen, Week 8 window for 8-week regimen, and Week 6 for 6-week regimen.

SVR₄ = HCV RNA < LLOQ in the SVR₄ window (4 weeks after the last actual dose of study drug) without any confirmed quantifiable (\geq LLOQ) post-treatment value before or during that SVR window.

SVR₁₂ = HCV RNA < LLOQ in the SVR₁₂ window (12 weeks after the last actual dose of study drug) without any confirmed quantifiable (\geq LLOQ) post-treatment value before or during that SVR window.

SVR₂₄ = HCV RNA < LLOQ in the SVR₂₄ window (24 weeks after the last actual dose of study drug) without any confirmed quantifiable (\geq LLOQ) post-treatment value before or during that SVR window.

Relapse₁₂ = confirmed HCV RNA \geq LLOQ between end of treatment and 12 weeks after last actual dose of active study drug (up to and including the SVR₁₂ assessment time point) for a subject with HCV RNA < LLOQ at Final Treatment Visit who completes treatment, excluding re-infection as described below.

Relapse₂₄ = confirmed HCV RNA \geq LLOQ during SVR₂₄ window among subjects who achieved SVR₁₂ and have data available during the SVR₂₄ window, excluding re-infection.

Relapse_{late} = confirmed HCV RNA \geq LLOQ at any time after the SVR₂₄ assessment time point for a subject who achieved SVR₂₄ and has post-SVR₂₄ HCV RNA data available, excluding re-infection.

Relapse_{overall} = confirmed HCV RNA \geq LLOQ between end of treatment and up to and including the last HCV RNA measurement collected in the PT Period for a subject with HCV RNA < LLOQ at Final Treatment Visit who completes treatment. Completion of treatment is defined as a study drug duration \geq 37 days, \geq 49 days and \geq 77 days for planned treatment duration of 6 week, 8 weeks and 12 week, respectively. Also, include a

summary of Relapse_{overall} for subjects who prematurely discontinued treatment, excluding re-infection.

For relapse analyses, the completion of treatment is defined as above. If the last available post-treatment value is \geq LLOQ, then the subject will be considered a relapse (i.e., will not require confirmation). Relapse analyses will exclude subjects who do not have any post-treatment HCV RNA values.

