10.7 Resistance Analyses

If possible, subjects treated with study drug during the Treatment Period who experience virologic failure will have resistance testing conducted if 1) they have on-treatment

breakthrough; 2) if they have post-treatment relapse (irrespective of the time of relapse), with a study drug duration \geq 77 days, 49 days and 38 days for 12-week, 8-week, and 6-week of treatment, respectively; or 3) if they have at least 6 weeks of treatment and fail to suppress by Week 6 (i.e., meet virologic stopping criteria). Subjects meeting one of these criteria will be referred to as subjects in the primary virologic failure (PVF) population, and a listing by subject that includes HCV subtype, IL28B genotype, reason for non-response, time point(s) sequenced as closest to time of VF, and HCV RNA value at the VF time point(s) will be produced for these subjects. In addition, all listings described below will display HCV subtype and reason for non-response in the subject identifier for each subject. A separate listing will delineate all subjects in the PVF population for whom no sequencing was performed (e.g., lost to follow-up while HCV RNA \leq 1000 IU/mL). Subjects treated with study drugs who do not achieve SVR₁₂ who do not meet the above criteria for the PVF population (e.g., those with less than 6 weeks of therapy who failed to suppress), but have a time point with HCV RNA \geq 1000 IU/mL after treatment discontinuation, will have the sample at that time point sequenced.

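### The SAP 4.2 rule that opens the 6-week Arm D counts only relapse, so on-treatment virologic failures in Arm C cannot hold it back; a separate cap is a cheap, optional improvement

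*SAP*

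**What the plan says.** SAP 4.2 plans about 10 genotype 2 subjects in Arm C (8 weeks) and about 10 in Arm D (6 weeks), without randomization. It gives one condition for opening the shorter arm: "Arm D would be launched if no more than one subject who completes treatment in Arm C experiences relapse through PT Week 4".

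SAP 10.1 keeps two kinds of virologic failure apart.
- Relapse can occur only "for a subject with HCV RNA < LLOQ at Final Treatment Visit who completes treatment". Completion of the 8-week course means at least 49 days of drug.
- On-treatment virologic failure is "breakthrough or failure to suppress during treatment (all on-treatment values of HCV RNA" at or above the LLOQ, the latter with at least 36 days of drug in the 8-week arm. SAP 10.1 lists it as its own reason for SVR12 non-response, and SAP 10.4 makes it a secondary endpoint beside relapse.

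A quantifiable value during treatment is confirmed by two consecutive values, "either both during treatment or at the final treatment measurement and the next consecutive post-treatment measurement". A single breakthrough value "followed by lost to follow-up will be considered a breakthrough (i.e., will not require confirmation".

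The supplied protocol covers Arms A and B only. Its section 5.6.1, on genotype 3, explains why relapse matters when a course is shortened: "treatment durations less than 12 weeks are predicted to result in a greater number of relapses".

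**The concern.** The rule decides whether about 10 new subjects receive a shorter course, on the strength of what happened on the longer one. A subject who fails while still on the 8-week course is evidence against shortening, yet falls outside the count. Such a subject is normally not below the LLOQ at the Final Treatment Visit, so cannot relapse by definition. The subject may also not be a completer: Protocol 5.5.1 stops drug in subjects who meet the virologic failure criteria, and SAP 10.7 points to a similar rule for the later arms, "if they have at least 6 weeks of treatment and fail to suppress by Week 6 (i.e., meet virologic stopping criteria".

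Three breakthroughs among ten Arm C subjects, with no relapse, would therefore satisfy the written condition. Each on-treatment failure also takes one subject out of the group that could relapse, so the rule becomes a little easier to pass as the longer course does worse.

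**Working it through.** **The plan's own figure.** The SAP gives no operating characteristic for the launch rule. Its only precision figure for an arm of this size is the Wilson interval at 9 of 10 (SAP 4.3). With z² = 3.8415, the centre is (0.9 + 3.8415/20)/(1 + 3.8415/10) = 0.7890 and the half-width is 1.96 × √(0.009 + 3.8415/400)/1.38415 = 0.1931. The interval is 59.6% to 98.2%, as stated.

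**Inputs.** n = 10 and a limit of one relapse (SAP 4.2). Assumed, because the documents give no genotype 2 rates: q, the probability of on-treatment virologic failure per dosed subject, and r, the probability of relapse by PT Week 4 among the rest. All the rest are taken to complete treatment, and on-treatment failures are taken never to count as relapses. One exception is ignored: a subject who breaks through, is suppressed again by the Final Treatment Visit, completes 49 days and then relapses would count, as a relapse.

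**Formulas.**
- Rule as written: Σ over k of Bin(k; 10, q) × P(Bin(10 − k, r) ≤ 1), which equals P(Bin(10, (1 − q)r) ≤ 1).
- Separate cap added: the same sum over k = 0 and 1 only.
- Pooled cap of one: P(Bin(10, q + (1 − q)r) ≤ 1).

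**Direction, at r = 5%.**
- q = 0: 0.95¹⁰ + 10 × 0.05 × 0.95⁹ = 0.5987 + 0.3151 = 0.914.
- q = 10%: (1 − q)r = 0.045, so 0.955¹⁰ + 10 × 0.045 × 0.955⁹ = 0.6310 + 0.2973 = 0.928.

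**Separate cap, at r = 5% and q = 5%.** k = 0 gives 0.5987 × 0.9139 = 0.5472, and k = 1 gives 0.3151 × 0.9288 = 0.2927. The sum is 0.840.

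**Launch probability, r = 5%.**

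| q | As written | Of which two or more on-treatment failures | Separate cap added | Pooled cap of one |
|---|---|---|---|---|
| 0% | 0.914 | 0 | 0.914 | 0.914 |
| 1% | 0.915 | 0.004 | 0.911 | 0.884 |
| 2% | 0.917 | 0.015 | 0.902 | 0.852 |
| 5% | 0.921 | 0.081 | 0.840 | 0.746 |
| 10% | 0.928 | 0.250 | 0.678 | 0.563 |

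The separate cap removes exactly the third column. At other relapse rates, the reduction at q = 1, 2, 5 and 10% is 0.004, 0.016, 0.085 and 0.261 for r = 2%, and 0.003, 0.013, 0.071 and 0.218 for r = 10%.

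**Timing.** The final on-treatment value is confirmed at the next post-treatment measurement. SAP Table 5, "Analysis Time Windows for HCV RNA, Resistance Endpoints, (Post-Treatment Period"), puts that at PT Week 2, before the PT Week 4 decision point. Failure to suppress is known by the end of treatment.

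**The case against.** **The governing text is missing.** Arms C to F come from an amended protocol that was not supplied. Launch conditions belong there, and it may hold a wider one. This stands, and it confines the point to the SAP 4.2 wording. SAP 12.1 lists only resistance updates as differences between the latest protocol and the SAP, which suggests, without proving, that the protocol's rule is the same.

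**Relapse is the right outcome for shortening a course.** On-treatment failure mainly reflects potency or adherence, and an early failure would occur at 6 or 8 weeks alike. This is a fair reason to keep relapse as the main condition. It does not explain why several failures on the longer course should have no bearing on opening the shorter one.

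**Oversight exists.** Protocol 5.1.2 plans ongoing review in an open-label study, and Protocol 5.4.1.2 lets the sponsor's physician stop enrollment in any arm on safety grounds. A reader might infer that nothing could stop Arm D. The documents do not support that. These powers are discretionary, however, and set no count. The interim analysis of Arms C to F (SAP 4.4.1) comes after Arm D has finished.

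**Size is assumed.** This stands. At 1 to 2% on-treatment failure, the chance of passing despite two or more such failures is only 0.004 to 0.015.

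**A pooled cap does more than close the gap.** This also stands. Under a single limit of one for both failure types, one breakthrough cuts the allowed relapses from one to zero. At r = 5%, the pooled cap lowers launch probability by 0.0313, 0.0650 and 0.1754 at q = 1, 2 and 5%. Of that, only 0.0040, 0.0153 and 0.0814 are cases with two or more on-treatment failures, so about 87%, 77% and 54% of the lost launches are other cases.

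**Conclusion.** The point holds as a gap in the scope of the launch rule: as worded in SAP 4.2, on-treatment virologic failure in Arm C cannot keep Arm D closed and slightly raises the chance of opening it. The size depends wholly on assumed rates. It is negligible at about 1% on-treatment failure, about 0.08 in launch probability at 5% (5% relapse), and nil if no such failure occurs.

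A reader might infer an analysis error, or that the SAP disregards on-treatment failure. Neither follows: SAP 4.2 does not conflict with the SAP 10.1 definitions, and SAP 10.4 reports on-treatment failure as a secondary endpoint. Nor do the documents show that the gap matters in practice, since they give no genotype 2 rates. This is a cheap improvement of low severity, for the sponsor to consider.

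**What to change.** Keep the relapse condition in SAP 4.2 word for word, make it a requirement (launch only if), and add a second condition:

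> *and no more than one dosed Arm C subject has on-treatment virologic failure (confirmed breakthrough, or failure to suppress as defined in SAP 10.1).*

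The word confirmed applies to breakthrough only, since failure to suppress is defined by all on-treatment values. It keeps out a single breakthrough value followed by loss to follow-up. If 2% of subjects had such a value and none had confirmed failure, counting them would lower launch probability from 0.917 to 0.902 at 5% relapse (the 2% row above). Separate caps also avoid mixing two standards in one count, because SAP 10.1 accepts an unconfirmed last post-treatment value as relapse.

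The addition does not cover unsuppressed subjects who stop before 36 days, or relapse in subjects with under 49 days of drug. The sponsor may choose a pooled cap of one instead, but should then describe it as a stricter rule that also tightens the relapse allowance.

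**Cost.** One added condition, with no new visit, no new data and no later decision date. A SAP edit alone may not bind enrollment, so the amended protocol should carry the same condition if it has none; that needs IEC/IRB approval (Protocol 9.1). The downside is that Arm D is held back somewhat more often, by the amounts in the table.

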4.3 Sample Size

It is planned to enroll approximately 70 subjects into this study. With a sample size of 10 subjects per arm and an observed SVR₁₂ rate of 90%, the 2-sided 95% confidence

interval, using Wilson's score confidence interval, will be (59.6%, 98.2%); With a sample size of 20 subjects per arm and an observed SVR₁₂ rate of 90%, the 2-sided 95% confidence interval, using Wilson's score confidence interval, will be (69.9%, 97.2%). Subjects who do not have data at PT Week 12 (after performing the described imputation) count as failures for SVR₁₂ so no adjustment for dropout is applicable.

From the perspective of safety assessment, the probability that a given adverse event would not be observed among 70 subjects is shown in the second column of [Table 1](#) for various true population incidence rates. With 70 subjects, the probability is at least 99.9% to observe an adverse event with an incidence rate of 10% or higher.

Table 1. Probability of Not Observing an Adverse Event or Lab Abnormality with 70 Subjects for Various True Incidence Rates

True Incidence Rate	Probability of Not Observing
0.10	< 0.001
0.20	< 0.001
0.30	< 0.001
0.40	< 0.001
0.50	< 0.001

4.4 Planned Analysis

All analyses will be conducted by statisticians and programmers at AbbVie or designee according to the methodologies specified in this SAP. There is no intention of stopping the study early based on efficacy findings from the interim analysis. The intention is to follow all subjects who receive active drugs for defined durations in each arm.

4.4.1 Interim Analysis

There will be an interim analysis after all enrolled subjects in Arms A and B have completed through Post-Treatment Week 12 or prematurely discontinued from the study, and another interim analysis after all enrolled subjects in Arms C, D, E and F have

completed through Post-Treatment Week 12 or prematurely discontinued from the study. For interim analyses, data will be locked after performing appropriate data cleaning.

Data collected after each interim analysis will be added to a new version of the database. At the end of the study, all data will be cleaned and locked and included in the final CSR.

